### 1. PROJECT TITLE

The Efficacy of Intra-oral Neuromuscular Stimulation Training on Snoring in Individuals with Primary Snoring

### 4. ESTIMATED DURATION OF THE STUDY

Up to 2 years

### 5. LAY LANGUAGE SUMMARY OR SYNOPSIS

Snoring is part of a spectrum of conditions called Sleep Disordered Breathing (SDB) which spans from Simple Snoring to Severe Sleep apnea. SDB and snoring has multiple underlying mechanisms but often the common pathway is excessive loss of muscle tone in the throat and pharynx. These patients may be amenable to upper airway muscle training exercises using neuromuscular stimulation techniques. Over the last decade, there have been several publications on the use of upper airway training exercises and electrical neurostimulation of the upper airway for treatment of Snoring and OSA. Based on this background, we seek to test the hypothesis that daytime upper airway tongue muscle training using transoral surface neuromuscular electrical stimulation (SnooZeal Device) may have benefits to patients with Simple Snoring.

### 6. SPECIFIC AIMS

#### Primary Objective:

Assess the efficacy of daytime trans-oral neuromuscular stimulation training on nocturnal snoring.

#### Secondary Objectives:

Assess the efficacy of daytime trans-oral daytime neuromuscular stimulation training on sleep quality and its safety.

#### Primary Endpoint:

- A. Reduction of 20 % in the percentage of time spent snoring at levels greater than 40 dB. This will be achieved using WatchPat (510K - K161579) sleep studies
- B. Reduction of 40% in bed partner VAS assessment of snoring.

#### Secondary Endpoints:

- A. Reduction in the Epworth Sleepiness Scale (validated hypersomnolence questionnaire) and Pittsburgh Sleep Index (validated sleep quality questionnaire with 7 domains).
- B. Assess safety of device (record and investigate adverse events, oral status and monitor device integrity through use)

### 7. BACKGROUND AND SIGNIFICANCE

Forty five percent of the male population snore, 25% habitually (daily). Sleep disordered breathing (SDB) (partial or total obstruction of the upper airway during sleep) is a spectrum of conditions (Fig 1) ranging from simple snoring to obstructive sleep apnea-hypopnea syndrome (OSAHS). The latter affects at least 4-6% of the population and is associated with increased incidence of hypertension, cardiac (heart attacks) and cerebral events (strokes). Although the gold standard of treatment for OSAHS is Continuous Positive Airway Pressure (CPAP), a variety of treatments are offered for simple snoring.

[figure not shown]

Figure 1: spectrum of sleep disordered related breathing ranging from simple snoring to severe obstructive sleep apnea syndrome (OSAHS: obstructive sleep apnea hypopnea syndrome, CPAP: continuous positive airway pressure)

Although there are several lifestyle practices associated with snoring (smoking, obesity, drinking etc.), a significant proportion of individuals may snore despite not being associated with these.

The most notable change that occurs in the physiology of humans during sleep is the reduction in the tone of the muscles and increased collapsibility of the throat (pharynx) and tongue. Notably, there is evidence to show that the collapsibility is significantly higher in patients who obstruct (OSAHS) and marginally higher in patients who snore (simple snoring) when compared to individuals who don't snore (Fig 2). As demonstrated in the graph below, it has been shown that when compared to "normal" individuals, the breathing passage in snorers and sleep apnea individuals collapses at a positive rather than negative airway pressure.

[figure not shown]
[figure not shown]

Figure 2: critical closing pressure in healthy subjects, snorers and patients with OSA (SDB-1 = snorers, SDB-2 = Sleep Apnea), (according to Isono et al. 2)

Research has demonstrated that increasing the pharyngeal muscle activity or tone, reduces the collapsibility of the airway as demonstrated by the graphs below (Figure 3). It is the reduction of throat/pharynx/tongue muscle tone that leads to this partial or complete obstruction.

Redrawn from Smith and Schwartz, *Sleep Apnea: Pathogenesis, Diagnosis and Treatment*, 2002

Figure 3: Upper airway collapsibility and critical closing pressure in sleeping individuals (according to Schwartz et al.)

Several studies have shown that implanting electrical nerve stimulators (for the tongue and limited numbers for diaphragm) are effective in treatment of OSA. However, these stimulators involve operations and implantation of the device. Furthermore, studies involving apnea-triggered nocturnal stimulation reportedly disturb the patient sleep by arousals due to the electrical stimulation. Also, similar to implanted pacemakers, there are multiple maintenance and logistic complications (battery replacement, unable to be in electromagnetic fields, cannot have other external electrical circuits attached, detected by external detection devices like airport security etc. etc.).

There is a considerable body of knowledge, literature and evidence to state that use of transcutaneous electrical stimulation in paralyzed or inactive limbs (muscles with low or absent muscle tone) significantly improves muscle power and tone recovery. Considering the muscles of the throat, pharynx and tongue are of the same muscle type as of the limbs (skeletal muscle), the hypothesis is electrical stimulation of the pharyngeal and tongue muscles would lead to a similar effect of increased resting muscle tone and muscle tone during sleep.

Studies show that training the upper airway muscles either by playing a wind instrument (didgeridoo) or oropharyngeal exercises can ameliorate moderate OSA and snoring. A recent meta-analysis demonstrated that oropharyngeal exercises provide a reduction in apnea-hypopnea index (AHI) of 50% in adults and decreases snoring. Oropharyngeal exercises are, therefore, a viable option to treat patients suffering from snoring and OSA. The presumption is that these changes are due to improvement in pharyngeal muscle tone.

In a placebo controlled randomized study of tongue stimulation for OSA, although the OSA index did not significantly improve, there was a significant reduction in the snoring. The number of snoring epochs decreased in the training group (baseline  $63.9 \pm 23.1$  epochs per hour versus  $47.5 \pm 31.2$ ;  $P < .05$ ).

Unlike the above-mentioned study, the SnooZel device uses an entirely intra-oral stimulation device with an aim of reducing snoring in individuals with primary snoring. The mouth piece will be placed with two electrodes below and two above the tongue for muscle stimulation, with no transcutaneous component as in the previous studies.

A preliminary study with this trial product has been undertaken in 27 patients in Germany. SnooZeal device was used twice a day for 20 minutes each time during the 6 week training period. The study showed that the mean snoring reduced from 6.4 to 3.1 ( $p=0.001$ ) on bed partner Visual analogue score rating of snoring ((6.4 to 2.7 in the primary snoring subgroup ( $p=0.001$ ) versus a drop from 6.6 to 3.6 in the mild OSA subgroup ( $p=0.001$ )). There was a statistically significant improvement in 2 of 7 components of the Pittsburgh Sleep Questionnaire inventory supporting an improvement the snorer's sleep quality with the use of the device. This study has been accepted for presentation and subsequent publication in Chest 2018.

## 8. PROGRESS REPORT

N/A

## 9. RESEARCH DESIGN AND METHODS

### Introduction to device

Indications: The Snoozeal transoral neurostimulation device is a prescription only, home use device. Its primary indication is for use in primary snoring.

The TMS system is to be a reusable device that produces muscular stimulation via electrodes connected to the tongue muscles. It is to be considered a single medical device with three components; one controller, a washable electrode mouthpiece, and a remote control/mobile application (Figure 4).

[figure not shown]

Figure 4. SnooZeal transoral neurostimulation device.

The mouthpiece is connected to the control unit via a USB port and Bluetooth connection is established between the control unit and remote control/app. This allows the remote control/app control over the current level and on/off functionality of the control unit and mouth piece.

The mouthpiece is placed in the mouth, with two electrodes located above and two electrodes below the tongue. The therapy consists of a series of pulse bursts with the basic characteristic of 6 secs burst and 4 seconds rest. During the 20 mins therapy period the pulse frequency will change every 5 mins in a defined sequence (through 3, 10, 20 and 3 Hz frequencies). The product is to be used once daily (20 min therapy session), during the day, for a period of six weeks to get the desired improvement.

## Research Method:

The study plans to investigate the change in snoring sound, sleep quality and the safe use of intraoral neuromuscular stimulation using SnooZeal device. After appropriate screening and assessment, the recruited participants will proceed through three phases of the trial. The Pre-Trial phase collects data on the pretreatment state of the participant, after which they will enter the Therapy phase where they use the device once daily for a six week period whilst continuing to record the required data. The participant will stop using the device at the end of this stage and have a follow up phase for two weeks, during which trial indices will continue to be recorded. The trial period for each participant will be 10 weeks.

### A. Screening

Participants will be identified from Queen's Hospital, Barking, Havering and Redbridge NHS Trust. There will be a screening phone call to ensure suitability based on an inclusion criterion and offer first line information about the trial. If suitable, patients will be given a written information sheet and invited to undertake a 2 day home sleep study (using WatchPAT). If the average AHI from these 2 days is below 15/h, the participants will be invited for a clinical examination.

### B. Recruitment visit

- Clinical airway examination by ENT surgeon (Appendix 5)
- Review of inclusion and exclusion criteria (section 10)
- Informed consent (Appendix 7)
- Inclusion into trial

### C. Pre-therapy period (day -14 to -1):

- Bed partner daily subjective assessment of snoring (Visual Analog Scale). Participant's bed partner will be required to complete daily visual analogue scoring of the participant's snoring, with 1 being "no snoring" and 10 being "intolerable snoring".
- Oral examination (Detailed examination by Dentists to document pretreatment oral state – Appendix 5)
- Participant and bed partner to complete sleep quality questionnaires (Pittsburgh Sleep Quality Index, Epworth sleepiness score and subjective sleep quality questionnaire) on Day -1 (Appendix 4)

### D. Therapy phase (day 1-42)

- Face-to-face meeting, instruction on use of the intraoral device
- Participant to use the Snoozeal device for 20 minutes once daily
- Bed partner daily subjective assessment of snoring (VAS)
- Participant daily assessment of side effects/adverse events and time of use
- Participant and bed partner to complete Sleep quality Questionnaires (Pittsburgh Sleep Quality Index, Epworth sleepiness score and subjective sleep quality questionnaire) at day 42
- Weekly follow up phone call from research team to confirm compliance. Compliance will also be cross checked using the total time of use recorded by the device.

### E. End of Therapy Review (day 43 – 49)

- Review of device integrity by visual inspection

- Oral examination (Detailed examination by Dentists to document pretreatment oral state – see examination record sheets – Appendix 5)
- Repeat Sleep Study – 2 night sleep study with WatchPAT

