#### F. Follow Up phase (day 43-56)

- Participant advised to stop using device
- Bed partner daily subjective assessment of snoring (VAS)
- Subject and bed partner to complete Sleep quality Questionnaires (Pittsburgh Sleep Quality Index, Epworth sleepiness score and subjective sleep quality questionnaire) at day 56

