### Snoring Sound

- 1) Objective: WatchPat Sleep study: Comparative analysis of % total sleep time spent snoring will be undertaken between the 2 day sleep study pre and post therapy phase. To ensure consistency, the WatchPAT microphone will be placed in the same position, just below the suprasternal notch, in both pre and post sleep studies.
- 2) VAS: Partner reported change will be assessed using VAS. Therapy efficacy will be based on statistical analysis of average VAS scores for the three periods – pre-therapy (2 weeks), therapy phase (last 2 weeks) and follow up phase (2 weeks).  
Although data will be collected for the whole of the six-week therapy phase, comparative analysis will be limited to the last two weeks of the therapy phase to exclude any transitional changes. The six-week therapy stage data will undergo temporal analysis to establish if there is a progressive change in the indices measured.
- 3) Number of nights sleeping together recorded in Subjective sleep quality questionnaire will be assessed for the pre-therapy, therapy phase and follow up phase.

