#### Statistical Considerations

Sample size: 50 participants

Data will be analyzed based on two tailed paired t-test, with 80% power.  $P < 0.05$  will be considered significant. Multiple regression analysis will be used to identify which of the following factors has a causal relationship with the outcome - age, sex, BMI, neck size, AHI group (<5 and 5-15) and clinical examination characteristics (Endoscopy staging, Muller Maneuver, Friedman Classification, Tonsil size)

Power analysis:

- AHI reduction >50% and AHI <10: sample size required 17,
- VAS change of 40%, (i.e. average snoring score to drop from 6.4 to 3.8 on 10 point scale): sample size required 4. Standard deviations extrapolated from Verse et al..
- To calculate the required sample size for the paired observations of pre and post treatment for proportion of sleeping time snoring more than 40 dB; first the correlation between proportions before and after treatment was estimated by using provided pilot data. The required sample size of the patients with snoring more than 40 dB was then calculated such that the one-sided statistical test would be able to detect 20% reduction in snoring time from 50% to 30% with 80% power. (See Appendix 1 for validation of parameters)

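### Does the open seven-day window for the repeat WatchPAT study (days 43–49, device already stopped) undermine primary endpoint A?

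*Protocol*

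**What the plan says.** All of this is in section 9 of the protocol unless stated otherwise.

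- **Therapy** runs from day 1 to day 42. Under Research Method: "The participant will stop using the device at the end of this stage and have a follow up phase for two weeks". The Follow Up phase (days 43–56) repeats this: "Participant advised to stop using device".
- **The post-therapy objective measurement** is listed under End of Therapy Review (days 43–49): "Repeat Sleep Study – 2 night sleep study with WatchPAT". No nights within the window are preferred.
- **The comparison for endpoint A** is set out under Snoring Sound, item 1: "Comparative analysis of % total sleep time spent snoring will be undertaken between the 2 day sleep study pre and post therapy phase".
- **The bed-partner VAS** is averaged over three periods in item 2: two weeks before therapy, the last two weeks of therapy, and two weeks of follow-up. Of the therapy phase it says "comparative analysis will be limited to the last two weeks of the therapy phase to exclude any transitional changes".
- **The rationale** in section 7 is that stimulation should produce "a similar effect of increased resting muscle tone and muscle tone during sleep".
- **The planning effect** for endpoint A, under Statistical Considerations, is to "detect 20% reduction in snoring time from 50% to 30% with 80% power", with 50 participants overall.

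**The concern.** Endpoint A has only one post-therapy reading, and how long each participant has been off the device at that reading depends on the appointment. The protocol is stricter elsewhere. Questionnaires are fixed to days -1, 42 and 56, and the VAS is split into an on-device and an off-device period. It can look as if the protocol guards against change over time for one primary measure and ignores it for the other.

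At stake would be dilution. If benefit fades within days of stopping, the mean fall is understated, more so for late appointments, and varied lags add some scatter. A device that works could then miss its target. Naming days 43–44 as target nights looks like a cheap remedy.

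**Working it through.** **Inputs from the protocol:** last therapy day 42; window days 43–49; two nights; n = 50; planned fall 50% to 30%, i.e. 20 points; two-sided paired t-test at 0.05.

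**Assumptions, because the protocol gives no figures:** the fade rate, the SD of the paired change, and how appointments spread over the window. The SD and pre/post correlation behind endpoint A are not stated, so the 50 cannot be reproduced for it. What can be checked is how far timing could matter.

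**1. Lag.** A night labelled day *k* has lag *t = k* − 42. The six consecutive night pairs have mean lags 1.5, 2.5, 3.5, 4.5, 5.5 and 6.5 days. Evenly spread, the mean is 24/6 = 4.0 days. With 80% on the first pair and 4% on each other pair it is 0.80 × 1.5 + 0.04 × 22.5 = 2.1 days.

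**2. Fall observed, and power.** Retained effect is 20(1 − *t*/*T*) for a linear fade to zero at *T* days, or 20 × 0.5^(*t*/*H*) for half-life *H*, averaged over the two nights. Under the 14-day linear fade the six slots give 17.86, 16.43, 15.00, 13.57, 12.14 and 10.71 points, with mean 14.29. Power uses the noncentral t with 49 degrees of freedom and noncentrality (mean/SD) × √50. Each cell shows even spread, then the 80% target.

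| Assumed fade | Mean fall, points | Gain | Power, SD 20 | Power, SD 30 | Power, SD 40 |
|---|---|---|---|---|---|
| None | 20.0 / 20.0 | 0 | >99.9% / >99.9% | 99.6% / 99.6% | 93% / 93% |
| Half-life 28 days | 18.1 / 19.0 | 0.9 | >99.9% / >99.9% | 98.7% / 99.2% | 88% / 91% |
| Linear, 28 days | 17.1 / 18.5 | 1.4 | >99.9% / >99.9% | 97.7% / 99.0% | 84% / 89% |
| Linear, 14 days | 14.3 / 17.0 | 2.7 | 99.9% / >99.9% | 91.0% / 97.5% | 70% / 84% |

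Example for the last row at SD 20: noncentrality = 14.29/20 × 7.07 = 5.05 against a critical value of 2.01, so power is 99.9%. If every participant were recorded in the latest slot (10.71 points), power would still be 96%.

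**3. Scatter from scheduling.** Under the 14-day fade with even spread, the slot-to-slot SD is 2.44 points. It inflates an SD of 10 by √(100 + 5.95)/10 − 1 = 2.9%, and an SD of 20 by √(400 + 5.95)/20 − 1 = 0.7%. With that inflation, power at SD 20 is 99.8%. Targeting lowers the scheduling SD only to 1.94, and if just 60% meet the target it is 2.46, no lower than at present.

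**4. The endpoint threshold, for a true fall of 20 points.** If the 20% in endpoint A means 20 points, every fading scenario falls short with targeting (17.0, 18.5, 19.0) and without it (14.3, 17.1, 18.1). If it means 20% of 50%, i.e. 10 points, every scenario passes, including the worst single slot at 10.7. With no fade, nothing changes. Targeting never changes the answer here.

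**5. The VAS rule.** Limiting the VAS comparison to the last two weeks of therapy drops the first four weeks, days 1–28. That removes build-up while the device is in use and says nothing about fading afterwards. For the off-device period the same item averages all 14 follow-up days, twice the length of the WatchPAT window. The protocol is therefore no stricter about off-device timing for the VAS than for endpoint A.

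**The case for a change.** The factual basis is sound: one two-night study, off the device, with no preferred nights. The strongest case takes harsher assumptions. With a half-life of 7 days and an SD of 40, power is 85% for days 43–44, 66% with even spread and 45% for the latest nights. A shorter half-life would cost more. The threshold result in step 4 also holds for a true fall of exactly 20 points. Under the 14-day linear fade, a true fall between 20/0.850 = 23.5 and 20/0.714 = 28.0 points would reach 20 observed points with targeting but not with even spread.

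That arithmetic stands, but it needs both rapid fading and either a large SD or a particular true effect, and the protocol supports none of these. Its training rationale points towards some persistence. With SD 30 and a half-life of 14 days or longer, power is at least 92% at any timing.

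Nor is the remedy free. After the instruction meeting the therapy phase lists no further visit, only "Weekly follow up phone call from research team to confirm compliance", so the recorder would have to be delivered or the review brought forward. It would also need a definition of the night of day 43, since the night following the day-42 session is earlier still.

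Two related requests, to record the study dates and to name the VAS period that decides endpoint B, ask for detail commonly left to the statistical analysis plan, which is not shown. They do not make the window wrong.

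**Conclusion.** The concern does not hold. The protocol does not contradict itself here: an off-device reading within a week of finishing a training course is a coherent way to test whether training changed nocturnal snoring, and the window is of ordinary width. The possible cost is 0 to 2.7 points of a 20-point fall across the scenarios tabulated, every non-zero value resting on an assumed fade rate and assumed scheduling. With n = 50 and an SD of change of 10 to 20 points, also assumed, power is at least 99.8% with or without preferred nights. A material loss needs rapid fading together with an SD around 40. Any dilution lowers the apparent benefit, so a positive result would be no less credible. Preferring the earliest nights is a reasonable scheduling choice, but the plan as written gives a sound reading of endpoint A in this respect.

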#### F. Follow Up phase (day 43-56)

- Participant advised to stop using device
- Bed partner daily subjective assessment of snoring (VAS)
- Subject and bed partner to complete Sleep quality Questionnaires (Pittsburgh Sleep Quality Index, Epworth sleepiness score and subjective sleep quality questionnaire) at day 56

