#### G. Post Therapy Review (day 57)

- Face-to-face meeting and feedback
- Collection of participant data sheets
- Participant subjective overall assessment

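### The two follow-up weeks are meant to be off-device and feed the VAS efficacy analysis, but the listed procedures rely on advice to stop and include no check of use

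*Protocol*

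**What the plan says.** Section 9 of the protocol describes a two-week baseline, six weeks of daily therapy and a two-week follow-up. Of the end of therapy, Research Method says "The participant will stop using the device at the end of this stage". Under F. Follow Up phase (day 43-56) the matching procedure is "Participant advised to stop using device", alongside the daily bed-partner VAS and the questionnaires at day 56.

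The follow-up scores are used. Under Snoring Sound, "Therapy efficacy will be based on statistical analysis of average VAS scores for the three periods", and the third of these periods is the two-week follow-up. Under Sleep Quality, the Epworth, Pittsburgh and subjective sleep-quality questionnaires are also assessed for the follow-up phase.

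Monitoring of use appears in D. Therapy phase (day 1-42). It consists of "Participant daily assessment of side effects/adverse events and time of use", a weekly compliance call, and the statement "Compliance will also be cross checked using the total time of use recorded by the device". After day 42 the items that concern the device or its records are "Review of device integrity by visual inspection" in section E and "Collection of participant data sheets" in section G.

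**The concern.** This appears to be a single-arm study: every participant goes through the same three phases. The follow-up fortnight is therefore the only period after therapy in which the trial can see what happens to snoring once stimulation stops. That reading depends on participants having stopped.

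Some may not stop. They are at home, no routine return of the device is listed, and those who feel a benefit have a reason to carry on. If some do, the follow-up VAS and day-56 questionnaires describe a mixture of on-device and off-device participants, and could look better than true off-device snoring and sleep. The absence of a rebound would then have two explanations, carry-over or continued use. This is a matter of data collection: if use is not recorded on those days, no analysis plan can supply it afterwards.

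**Working it through.** The point rests mainly on setting the text side by side. The protocol gives no figure of its own to reproduce.

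**Step 1: are days 43-56 inside the study?** Day -14 to -1 is 14 days, day 1-42 is 42 days and day 43-56 is 14 days. 14 + 42 + 14 = 70 days = 10 weeks, which matches the trial period stated in Research Method. Section 17 lets participants go on using the device once the study is complete. That permission therefore does not cover days 43-56.

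**Step 2: what is listed for each period?**

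| Period | Intended device status | Use checks listed |
|---|---|---|
| Day 1-42 (D) | Once daily | Daily time-of-use record, weekly call, device-counter cross-check |
| Day 43-49 (E) | Off | None; visual inspection of the device |
| Day 43-56 (F) | Off | None; advice to stop |
| Day 57 (G) | Study visit | None; data sheets collected |

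The only device return in the protocol is for a defective unit (section 15, Device Defects). No date is given for reading the counter, and the protocol does not say whether the device stores dated sessions.

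**Step 3: could the listed data separate the two explanations?** Take the planning values in Statistical Considerations, a VAS of 6.4 falling to 3.8, a difference of 2.6. Let c be the share of participants still using the device in follow-up, and r the share of the benefit kept by those who stop. Both are assumptions; the protocol gives neither. Assume also that continuing users stay at 3.8. Then

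follow-up mean = 6.4 - 2.6 × [c + (1 - c) × r].

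- c = 0, r = 0: 6.40 (everyone stops, full rebound)
- c = 0.2, r = 0: 6.4 - 0.52 = 5.88; c = 0, r = 0.2: also 5.88
- c = 0.5, r = 0: 6.4 - 1.30 = 5.10; c = 0, r = 0.5: also 5.10
- c = 1, or r = 1: 3.80

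Each intermediate mean arises equally from continued use or from carry-over. Without a measure of c, the follow-up VAS cannot say which. The example shows only that the two cannot be separated; it does not estimate a bias.

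**Step 4: what is untouched?** The VAS comparison of the pre-therapy fortnight with the last two therapy weeks uses no data after day 42. The objectives and endpoints in section 6 include none on durability.

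**The case against.** The strongest reply is that nothing here is contradictory. The protocol says participants will stop and then tells them to, and an instruction is the usual way to end self-administered treatment at home. On that view the point asks for one more monitoring step. It is fair that there is no contradiction. The request still has substance, because it supplies data needed to interpret a period that the protocol itself uses for efficacy.

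A second reply is that use may be recorded after all. The same Research Method sentence says the trial's measures go on being recorded during follow-up, data sheets are collected at day 57 rather than day 43, and some record sheets and appendices are not shown. This stands. A reader might infer that no use data will be collected after day 42; the text supports only that none are listed, and section F names only the VAS and questionnaires.

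Two stronger readings are also tempting:

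- **Continued use could be hidden in the counter total.** A reader might infer that missed therapy sessions and later sessions could cancel out. That needs a single, late, undated reading and an over-reported diary. The protocol states none of these, and the natural place for the cross-check is during or at the end of therapy. A reading then would still say nothing about the days after it.
- **The primary sleep-study endpoint is compromised.** The repeat "2 night sleep study with WatchPAT" falls in days 43-49, so a reader might infer that continued use would bias endpoint A. The device is used by day, and endpoint A is not defined as an off-device measure. The documents do not support that step.

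**Conclusion.** The point holds as a minor design improvement. Follow-up is intended to be off-device and its VAS and questionnaires are analysed, yet the listed procedures neither prevent nor detect use in days 43-56. A maintained improvement in follow-up should therefore not be read as carry-over on the listed data alone.

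The size is unknown. The conclusion rests on the listed procedures being complete and on continued use being plausible; the protocol gives no evidence of how often it would occur. Nor does it say who holds the device in those two weeks, although the absence of a listed return and the offer of later use fit with its staying with the participant. A reader might go further and infer that the VAS efficacy result as a whole is unreliable. That does not follow, because the main on-therapy comparison does not depend on follow-up.

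**What to change.** Use the two visits already planned, and choose one of these:

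- **Hold the device.** Take it in at the end-of-therapy review, scheduled as near day 43 as possible, and hand it back at day 57 to those who wish to continue.
- **Read the counter twice.** Record and date total time of use at that review, as near day 43 as possible, and again at day 57. The difference is use between the two readings. If the device or app stores dated sessions, one download at day 57 is enough.

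A review held late in the day 43-49 window leaves the days before it uncovered under either option, unless sessions are dated.

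Report follow-up use beside the follow-up VAS and questionnaires. Keep all participants in the main comparison. Show results without continued users only as a sensitivity analysis, because the decision to continue may depend on perceived benefit and excluding those people would select on outcome.

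The cost is small: participants bring the device to day 57, or are without it for up to two weeks in which they are not meant to use it. The change should be made before enrolment.
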